### Dosing

The initial daily dose will be determined from the initial prescription and calculated based on a formula using strength, quantity, and days supply in the claims. Dose during the index hospitalization can also be captured for the subset of patients with medical chart review.

### Follow-up

At least 3 months and no more than 12 months after the index hospitalization discharge date or until death, if sooner.

Health Care Resource Utilization

Medical Encounters

Medical encounters will be classified into the following categories of health care services:

- Inpatient admissions will be defined as hospitalizations during the study period

<sup>1 Berenson K, Casciano R, Makenbaeva D, Mozaffari E, Lamerato L, Corbelli J. Economic consequences of severe bleeding in patients with acute coronary syndrome in the USA. *Adv Ther*. 2010;27(8):564-579.

<sup>2 The run-out date will be defined as the pharmacy claim date + days supply.

- *Emergency department visits* will be defined as visits to emergency treatment centers or hospital emergency rooms during the study period
- *Ambulatory visits* will be defined as the following encounters during the study period:
  - office visits to primary or specialty care providers, urgent care clinics
  - outpatient hospitals visits
  - other ancillary settings including laboratory, radiology, and physical therapy
- *Pharmacy fills* will be defined as outpatient filled prescriptions (including initial fills and refills) during the study period

### All-cause Medical Encounters

Medical encounters associated with primary or secondary diagnosis and procedure codes for all services during the study period.

### Disease-related Medical Encounters

Medical encounters associated with the diagnosis and treatment of CV events and their associated sequelae (e.g., MI, revascularization, stroke, unstable and stable angina, congestive heart failure, and bleeding; to be further defined in the SAP).

### Health Care Costs

### All-cause Medical and Pharmacy Costs

Health care costs will be computed as the combined health plan and patient paid amounts for all services during the study period. Costs will be calculated for inpatient admissions, emergency department visits, ambulatory care visits (including physician office visits, outpatient hospital visits and other ancillary services), and outpatient pharmacy fills. Total costs will be calculated as the sum of all medical and pharmacy costs. Disease-Related Medical Costs

The health plan and patient paid amounts for medical encounters associated with the diagnosis and treatment of CV events and their associated sequelae (e.g., MI, revascularization, stroke, unstable and stable angina, congestive heart failure, and bleeding; to be further defined in the SAP).

### Disease-Related Pharmacy Costs

The health plan and patient paid amounts of outpatient pharmaceuticals for treating CV events and their associated sequelae including, but not limited to antiplatelet agents and anticoagulants.

\**Note*: All costs will be adjusted using the annual medical care component of the Consumer Price Index (CPI) to reflect inflation between study start and end dates.

### Index Admission Date

The index admission date will be defined as the admission date of the index hospitalization.

### Index Hospitalization

First hospitalization during the selection window with a primary or secondary ACS diagnosis code, PCI procedure code, and at least one claim for prasugrel or clopidogrel within 30 days post-discharge. For subjects with multiple hospitalizations during the selection window, the first such hospitalization will be selected as the index hospitalization to maximize the available follow-up.

#### Index Hospitalization Treatment

The administration of ADP-ri, aspirin, and other treatments during the index hospitalization will be identified in the subset of patients with medical chart review.

#### Index Hospitalization Length of Stay

Total number of days during the index hospitalization, inclusive of admission and discharge dates.

### ICU/CCU

An intensive care unit (ICU) or coronary care unit (CCU).

#### Major Adverse Cardiovascular Event(s) (MACE)

MACE is a composite endpoint of CV events that has been widely used in the CV literature to characterize the overall efficacy or effectiveness of treatment. In this study, MACE will be defined as a composite measure based on the presence of any evidence for all-cause mortality, hospitalization for stroke, rehospitalization for myocardial infarction or unstable angina, or post-discharge revascularization (PCI or CABG).

#### Myocardial infarction (MI)

A cluster of events with coronary artery disease complicated by an acute intracoronary thrombus including ST elevation myocardial infarction (STEMI) or non-ST elevation myocardial infarction (NSTEMI).

### Net Adverse Clinical Event(s) (NACE)

The term NACE has been used in prior studies to characterize the net balance for CV drugs which typically reduce MACE at the expense of increased bleeding. In this study, NACE will be defined as a composite measure based on the presence of any evidence for a MACE event, *or* hospitalization for bleeding.

#### Overall treatment duration

The number of days between the first fill and the run-out date of last fill for the post-discharge index therapy.

<sup>3 Rao SV, Dai D, Subherwal S, Weintraub WS, Brindis RS, Messenger JC, Lopes RD, Peterson ED.

Association Between Periprocedural Bleeding and Long-Term Outcomes Following Percutaneous Coronary Intervention in Older Patients. *JACC Cardiovasc Interv.* 2012; 5(9):958-65. doi: 10.1016/j.jcin.2012.05.010.  Vetrovec et al. Prasugrel Compared to Ticagrelor in Acute Coronary Syndrome Patients Treated with a Percutaneous Coronary Intervention: Findings from a Large Hospital Charge Master Database. Accepted for presentation at the SCAI 2014 Scientific Sessions in Las Vegas, NV May 28-31, 2014

<sup>5 Harjai KJ, Shenoy C, Orshaw P, Usmani S, Judy Boura J, and Mehta RH. Clinical Outcomes in Patients with the Concomitant Use of Clopidogrel and Proton Pump Inhibitors After Percutaneous Coronary Intervention: An Analysis From the Guthrie Health Off-Label Stent (GHOST) Investigators. *Circ Cardiovasc Interv.* 2011; 4:162-170. doi:10.1161/CIRCINTERVENTIONS.110.958884

#### Persistence

Persistence estimates the amount of time that subjects continuously filled prescriptions before a 30-day gap in therapy or the end of the study period. Persistence with the post-discharge index therapy will be calculated as the number of days from the study index date to the date of discontinuation.

#### Post-discharge Index Therapy

The first fill for prasugrel or clopidogrel within 30 days after discharge from the index hospitalization.

#### Post-discharge Index Therapy Fill Date

The date of the first fill for the post-discharge index therapy.

#### *Post-PCI length of stay*

The difference in days between the PCI procedure and discharge during the index hospitalization for the subset of patients with medical chart review.

#### Prescriber specialty

The physician specialty on the first pharmacy claim for the post-discharge index therapy will be identified. The physician specialty on the discharge medications will be identified for the subset of patients with medical chart review.

#### Quan-Charlson Comorbidity Index

The Quan-Charlson comorbidity index is an update of the Charlson comorbidity score and serves as a proxy for the cumulative likelihood of one-year mortality or the burden of comorbidity. The index contains 17 comorbid conditions identified using primary and secondary ICD-9 diagnosis codes during the baseline period (see Annex 1). Each of the 17 conditions is assigned a weight or score of 1, 2, 3, or 6 depending on the risk of death associated with the condition. The overall comorbidity score is the sum of associated weights for any of the 17 conditions present during the baseline period (maximum possible score of 29). The Quan-Charlson comorbidity score will be grouped into the following categories: 0-1, 2, 3, and 4+.

#### Rehospitalization/Readmission

An inpatient admission following the index hospitalization.

<sup>6 Charlson ME, Pompei P, Ales KL, MacKenzie CR. A new method of classifying prognostic comorbidity in longitudinal studies: development and validation. *J Chron Dis.* 1987; 40:373-83.

<sup>7 Quan H, Sundararajan V, Halfon P, Fong A, Burnand B, Luthi JC, et al. Coding algorithms for defining comorbidities in ICD-9-CM and ICD-10 administrative data. *Medical Care*. 2005; 43:1130-39.

#### Revascularization

A coronary vessel procedure with the goal of restoring or improving perfusion to the heart following ischemia, via coronary artery bypass surgery (CABG) or percutaneous coronary intervention (PCI).

#### Selection Window

Timeframe for identifying the index hospitalization: 01 September 2009 to 31 May 2013.

#### Stent thrombosis

Evidence of death or a myocardial infarction within 30 days after stenting will be considered a probable stent thrombosis (adapted from the Academic Research Consortium [ARC] definition).

#### Study Index Date

The study index date will be defined as the discharge date of the index hospitalization.

#### Study Subjects

Subjects treated with prasugrel or clopidogrel within 30 days post-discharge from an ACS-PCI hospitalization.

#### Switching

Switching will be defined by presence of a prescription for an alternative ADP-ri, not the postdischarge index therapy.

#### Time to Post-discharge Index Therapy

The time to first index therapy fill post-discharge will be calculated by subtracting the index hospitalization discharge date from the index therapy fill date, inclusive of the index hospitalization discharge date.

<sup>8 Cutlip DE, Windecker S, Mehran R, et al.. Clinical end points in coronary stent trials: a case for standardized definitions. *Circulation*. 2007 May 1;115(17):2344-51.

## 5. Abstract

- Title: One Year Post-discharge Clinical and Economic Outcomes among Patients with ACS Managed with PCI and Treated with Prasugrel vs. Clopidogrel
- Rationale and background: While the results from the TRITON-TIMI 38 established the superior anti-thrombotic efficacy of prasugrel in combination with aspirin over clopidogrel plus aspirin, there is currently insufficient long-term real-world data that directly compares the clinical and economic outcomes of prasugrel and clopidogrel patients. This retrospective claims database analysis supplemented with a medical chart review for a subset of patients will help to fill in this important gap in the literature.
- Research Objectives: The primary study objective is to compare major adverse cardiovascular events (MACE) up to one year of hospital discharge among ACS patients with no history of TIA or stroke, managed with PCI, and treated with prasugrel vs. clopidogrel. Secondary objectives are to compare demographics, baseline clinical characteristics, treatment patterns, and clinical and economic outcomes up to one year of hospital discharge among ACS patients with no history of TIA or stroke, managed with PCI, and treated with prasugrel vs. clopidogrel.
- Study design: Retrospective cohort study
- Population: The primary study population will include ACS patients with no history of TIA or stroke, managed with PCI, and treated with prasugrel vs. clopidogrel. Subgroups with other important characteristics (age, gender, comorbidities of interest) will be defined in the SAP.
- Variables: The primary dependent variable will be major adverse cardiovascular events (MACE) through one year of hospital discharge. Secondary dependent variables will include clinical and economic outcomes, and treatment patterns during index hospitalization and through three months and one year post-discharge from the index hospitalization. Study timeframes will be finalized in the SAP. The primary independent variable will be treatment cohort (prasugrel vs. clopidogrel) and other independent variables (covariates) will include demographics, baseline clinical characteristics, and baseline treatment utilization.
- Data sources: Optum Research Database supplemented with medical chart review for a subset of patients.
- Study size: Refer to section 9.4 for preliminary sample sizes in the Optum Research Database (ORD). Final sample size will be known after applying all selection criteria.
- Data analysis: Descriptive analyses will be reported for all baseline variables (via appropriate measures of central tendency and inferential statistics where appropriate). Unadjusted cohort differences will be assessed using appropriate inferential statistics. Propensity score adjustment (matching or stratification) will be used to adjust for potential confounding bias. Primary and secondary outcomes will be assessed using multivariate analyses. Sensitivity

analyses will be employed as appropriate to assess the robustness of the results to the potential for unmeasured confounding and other statistical assumptions.

# 6. Amendments and Updates

Not applicable.

# 7. Rationale and Background

The American Heart Association's 2014 update of Heart Disease and Stroke Statistics showed that there were 1.14 million acute coronary syndrome (ACS)-associated hospital discharges in the United States (US) in 2010. Of the total hospitalizations, about 70% had diagnoses for myocardial infarction (MI), while approximately 30% were associated with unstable angina (UA). ACS patients are managed either invasively with percutaneous coronary intervention (PCI) with or without a stent, surgically with coronary artery bypass graft (CABG), or medically without revascularization. The use of a P2Y12 receptor inhibitor is recommended by current treatment guidelines as a standard component of an antiplatelet regimen, generally in combination with low dose aspirin, for the follow-up treatment of patients with ACS.

Prasugrel, a P2Y12 receptor inhibitor, was approved by the US Food and Drug Administration (FDA) in July 2009 for the reduction of thrombotic cardiovascular events (including stent thrombosis) in patients with ACS and managed with PCI. The TRITON-TIMI 38 trial, a randomized clinical trial (RCT) of 13,608 patients with ACS and managed with PCI (ACS-PCI), compared prasugrel to clopidogrel, both in combination with aspirin, and found that, as a more potent antiplatelet agent, prasugrel reduced the combined rate of death from cardiovascular causes, non-fatal myocardial infarction, or nonfatal stroke over a 15-month period (composite primary endpoint rate was 12.1% for clopidogrel vs. 9.9% for prasugrel; hazard rate for prasugrel vs. clopidogrel: 0.81; 95% CI: 0.73-0.90; p<0.001).

RCTs have high internal validity, and when done well, can best assess causation, or the impact of an intervention on outcomes. However, the generalizability of RCT study results to a broader patient population is often challenging due to restrictive study inclusion criteria. Retrospective claims database analyses can offer insights about the clinical and economic outcomes of a broader range of patients in usual care treatment settings, but results may be biased due to residual confounding from known and unknown factors (i.e., factors that influence both the intervention and outcome, and complicate assessments of causation).

TRANSLATE-ACS is an on-going observational study following more than 12,000 MI-PCI patients prospectively. This study is gathering rich clinical data through one year, but requires informed consent and relies on self-report for treatment adherence and cost outcomes. Another recent retrospective cohort study selected ACS-PCI patients on the basis of the prasugrel US prescribing information using the Premier database of hospital discharges. This study found marked differences in the profile of patients receiving prasugrel compared to clopidogrel. Prasugrel patients were younger and had a lower risk of comorbid conditions associated with bleeding. After adjustment for baseline differences, patients using prasugrel, compared to clopidogrel, had a significantly lower rate of MI-related rehospitalization with no increase in the rate of bleeding-related rehospitalization at 30 days and 90 days following the index ACS-PCI hospital discharge. The study also found that patients using prasugrel had significantly shorter length of stay and lower costs with no increased rate of bleeding during the index hospitalization. While results from this study, particularly those related to the reduction in MI, reflect the short term efficacy noted in the TRITON-TIMI 38 trial, long term observational data (> 90 days) comparing the use of these agents in the real world setting is scarce. The current retrospective claims database analysis will help fill this important gap in the literature as well as collect economic data from a large managed care health plan in the US.

# 8. Research Objectives

The overall hypothesis of this study is that, after adjustment for baseline differences, prasugrel will be associated with a significantly lower risk of major adverse cardiovascular events (MACE) than clopidogrel up to one year post-discharge from the index hospitalization.

### 8.1. Primary Objectives

1. To compare MACE with prasugrel versus clopidogrel up to one year post-discharge from the index hospitalization.

### 8.2. Secondary Objectives

- 2. To compare demographics and baseline characteristics between patients treated with prasugrel versus clopidogrel before propensity adjustment.
- 3. To compare index therapy treatment patterns with prasugrel versus clopidogrel including adherence, discontinuation, persistence, and switching as listed in Table 1 through 1) three months and 2) one year post-discharge from the index hospitalization.
- 4. To compare NACE and its components with prasugrel versus clopidogrel including bleeding as listed in Table 1 through 1) 30 days, 2) three months, and 3) one year post-discharge from the index hospitalization.
- 5. To compare all-cause health care resource utilization (including length of stay of the index hospitalization and subsequent readmissions) and costs with prasugrel versus clopidogrel through 1) 30 days, 2) three months, and 3) one year post-discharge from the index hospitalization. Resource utilization and costs will be stratified as listed in Table 1.
- 6. To compare disease-related (including MI, revascularization, stroke, unstable and stable angina, congestive heart failure, and bleeding as listed in Table 1) health care resource utilization and costs with prasugrel versus clopidogrel through 1) 30 days, 2) three months, and 3) one year post-discharge from the index hospitalization.
- 7. If differences in treatment patterns (i.e, adherence, persistence, switching, and discontinuation) are found, then assess factors associated with adherence, persistence, switching, and discontinuation of a) prasugrel and b) clopidogrel patients through one year post-discharge from the index hospitalization.
- 8. If differences in treatment patterns are found, then examine associations between treatment patterns (adherence, persistence, switching, and discontinuation) and outcomes (clinical: all-cause mortality, MACE, inpatient readmissions; economic: total costs) for a) prasugrel and b) clopidogrel patient through one year post-discharge from the index hospitalization.

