#### Adherence

Adherence with the post-discharge index therapy will be estimated using the proportion of days covered (PDC) during two specified time intervals: 3 months and 12 months post-discharge index therapy initiation. PDC will be calculated by dividing the total days supply of filled medications during the 3- and 12-month intervals by 90 and 365 days, respectively. For purposes of this study, the days supply of overlapping fills will be pushed out to start the day after the end of the previous fill's supply. The calculation will be corrected for inpatient admissions, under the assumption that during a hospitalization medication was supplied by the facility. PDC  $\geq 80\%$  will be considered adherent.

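### Objective 8's only economic outcome, total cost, contains the payments for the fills that define adherence and persistence; medical cost should be reported beside it

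*Protocol*

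**What the plan says.** Protocol 8.2, item 8, applies only if treatment patterns are found to differ. It will then "examine associations between treatment patterns (adherence, persistence, switching, and discontinuation) and outcomes", separately in the prasugrel and clopidogrel patients, over one year. The list of outcomes is closed: "outcomes (clinical: all-cause mortality, MACE, inpatient readmissions; economic: total costs". No other economic outcome is named.

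The definitions in section 3 fix both sides of that association.

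- **Outcome.** Under All-cause Medical and Pharmacy Costs, costs are the "combined health plan and patient paid amounts for all services during the study period", and "Total costs will be calculated as the sum of all medical and pharmacy costs". Pharmacy fills are "outpatient filled prescriptions (including initial fills and refills) during the study period", so fills of the index drug count.
- **Exposures.** "PDC will be calculated by dividing the total days supply of filled medications during the 3- and 12-month intervals by 90 and 365 days", with a correction that treats inpatient days as supplied by the facility, and a cut-off of 80%. Persistence is "calculated as the number of days from the study index date to the date of discontinuation". Discontinuation is the run-out of supply before the first gap of 30 days or more in index-therapy fills.

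Table 1 (section 9.2) lists total, medical and pharmacy costs separately, but that row is labelled for objectives 6 and 7, and no row is labelled for objective 8. None of the sensitivity analyses in 9.6.6 separates index-drug payments from other cost.

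**The concern.** The paid fills of the index drug enter the exposure as days supplied and the outcome as dollars. Among patients with identical medical use, the more adherent or persistent patient has the higher total cost, simply because more drug was bought. The total-cost association is thus a sum of two things: what the extra drug cost, and whatever change in the cost of care goes with staying on treatment. The first is set by price and carries no information about outcomes.

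A reader of objective 8 will naturally want to know whether patients who stay on treatment cost less to look after. With total cost as the only economic result, a small positive association could mean higher medical cost, no difference in medical cost, or a medical saving smaller than the drug bill. Price may also change within the clopidogrel analysis: 9.6.6 dates the generic to May 2012, inside the selection window of 01 September 2009 to 31 May 2013.

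**Working it through.** The protocol contains no cost, price or cost-related sample size figure, so there is no plan figure to reproduce on this point. Its only power statement concerns MACE and does not bear on objective 8. All dollar values below are assumptions.

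**Step 1: decomposition.** From the section 3 definitions,

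total cost = medical cost + other pharmacy cost + index-drug cost.

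PDC is index-drug days supplied divided by 365, so at price p per day, index-drug cost is about 365 x PDC x p. Between two groups,

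difference in total cost = difference in medical cost + difference in other pharmacy cost + 365 x (PDC difference) x p.

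The last term is positive whenever the first group is the more adherent.

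**Step 2: size of the built-in term.** For a PDC difference of 0.5 over one year:

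| Assumed price per day | 365 x 0.5 x p |
|---|---|
| $0.25 | $46 |
| $1 | $182 |
| $3 | $548 |
| $6 | $1,095 |
| $8 | $1,460 |

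**Step 3: the planned 80% cut-off.** A contrast of 0.5 is illustrative; the plan dichotomises PDC at 80%. A simulation used 5,101 patients (the prasugrel count in Table 2), 200 replicates, gamma-distributed medical cost with mean $15,000 in the non-adherent, a skewed PDC distribution, and no other pharmacy cost. The built-in drug difference between adherent and non-adherent patients was about $30, $122, $366, $732 and $975 at $0.25, $1, $3, $6 and $8 per day. This corresponds to a mean PDC gap of 732 / (365 x 6) = 0.334.

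Some results follow. The medical differences deviate slightly from the saving put in, through simulation error.

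| Price per day | Medical saving put in | Medical difference | Drug difference | Total difference |
|---|---|---|---|---|
| $0.25 | $500 | -$475 | +$30 | -$445 |
| $3 | $500 | -$473 | +$366 | -$107 |
| $6 | $500 | -$501 | +$732 | +$231 |
| $6 | $2,000 | -$1,983 | +$732 | -$1,251 |

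**Step 4: when the sign changes.** With other pharmacy cost equal, a medical saving S shows as a total-cost saving if S exceeds 365 x (PDC difference) x p, and as a total-cost increase if it falls short. At $6 per day under these assumptions the break-even is about $732. The medical-cost column recovers the saving at every price, because it contains no outpatient drug payments.

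**Step 5: limits of the formula.** It is approximate for PDC, since inpatient days are credited as covered with no paid fill. It is looser for discontinuation: a patient may refill after the first 30-day gap, and section 9.8 counts a switch as a discontinuation although a switcher goes on filling another ADP-ri. It does not carry over to switching itself, where one drug's payments replace another's.

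**The case against.** The strongest reply is that nothing here is an error. Total cost is the figure a payer cares about, drug spending is a real cost of staying on treatment, and item 8 promises only to examine associations; it claims no medical cost offset. MACE and inpatient readmissions are outcomes of the same objective and contain no drug cost, so a benefit of staying on treatment can be seen there. Medical and pharmacy costs are built separately anyway, the objective is secondary and conditional, and a SAP could add the split. All of this stands as a limit on how much weight the point can bear. It does not remove the point: the protocol states objective 8's economic outcome outright rather than deferring it, and readmissions and MACE are not in dollars.

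Three stronger readings are tempting and are not supported.

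- A reader might infer that higher adherence means higher total cost by construction and that any medical saving is masked. Only the drug component rises by construction. Savings are diluted, and in the simulation a $2,000 saving at $6 per day still appeared as about -$1,251.
- A reader might infer that the analysis says nothing about cost. It does answer the question for total cost; what it cannot do is split that total.
- A reader might infer a flawed comparison of prasugrel and clopidogrel slopes. Item 8 is run within each drug and states no test between them, and 9.6.6 lists an optional analysis before and after generic clopidogrel.

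**Conclusion.** The coupling is real and follows from the protocol's own definitions. Objective 8's sole economic outcome includes payment for the fills that define adherence, persistence and discontinuation, so by itself it cannot distinguish drug spend from the cost of care. How much this matters depends on prices and medical costs that the protocol does not give. Over the assumed $0.25 to $8 per day, the built-in term at the 80% cut-off ran from about $30 to $975 a year, which is minor at the bottom of the range and enough to reverse a saving of several hundred dollars at the top.

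Total cost should stay as a valid net figure. The primary endpoint, the other clinical outcomes of objective 8 and the cohort cost comparisons in objectives 5 and 6 are not touched. This is an inexpensive improvement to a conditional secondary objective, not a fault that invalidates it.

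**What to change.** In section 8.2, item 8, keep total costs and add total medical costs as a co-reported economic outcome for all four treatment patterns. Medical cost is already listed in Table 1, and 9.6.5.2 already specifies a model for it. State that the total-cost association is to be read beside the medical-cost one.

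Optionally add total costs net of payments for the index therapy. For switching, that measure should be net of all ADP-ri payments, because the drug switched to would otherwise stay in.

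Replacing total cost, or resting every cost statement on the net measures alone, is not needed: that would trade away the payer's net figure.

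The cost is one sentence in the protocol and one or two more secondary models per analysis on data already built, with correspondingly more secondary estimates to report.
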